## **3.2. Endpoints**

### **3.2.1. Primary Efficacy Endpoint:**

The primary efficacy endpoint will be the responder rate at EOS visit.

Responders are defined as patients with either:

- \* No change or decrease in the adjusted INCAT disability score and without any change in CIDP treatment between baseline and EOS visit.  
or
- \* An increase by 1 point in the adjusted INCAT disability score without requirement of any change in CIDP treatment between baseline and EOS visit.

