#### 4 STATISTICAL ANALYSIS

##### 4.1 DISPOSITION OF PATIENTS

In order to describe the population, descriptive statistics (number, or number and percentages) will be provided for the following:

- Patients screened (patients who signed informed consent)
- Patients enrolled
- Patients with a screening failure
- Patients who received study treatment (TTS)
  - Patients participating in the ancillary study
  - Patients who completed the study
  - Patients withdrawn early from the study and reasons for study discontinuation [AE, Protocol deviation, Withdrawal of consent, Lost to follow-up, Insufficient response to IMP, Other]  
Patients withdrawn early due to insufficient response of IMP with reason for insufficient response (INCAT, MRC sum score, R-ODS, Grip strength, CGI-Patient, CGI-Investigator, Clinical examination, Premature termination of IMP) and follow-up treatment (IVIg, Corticosteroids, Immunomodulatory or immunosuppressive agent or Other)
- Patients included in the FAS
- Patients included in the PPS

A separate in-text summary table will be produced to contain the following information: patients who received at least one dose of IMP in I10E-1302; non-responders in I10E-1302; responders in the study; and patients who discontinued. An in-text listing with all patients who were discontinued due to "Insufficient response to the IMP" may be produced. The said listing will contain identifiable relapse risk information based on review of efficacy and safety information.

Except for patients enrolled and patients with a screening failure, percentages will be calculated using the number of patients of the TTS as the denominator. For screen failure patients, a listing will be produced with the reason for screening failure and the specifications provided by the investigator. For patients who discontinued the study, a listing will be produced with the reasons of study discontinuation and the specifications provided by the investigator.

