#### 4.6 EFFICACY ANALYSES

The efficacy analyses will be performed on the FAS. The analyses of the primary endpoint will be repeated on the PPS as sensitivity analysis (only if the PPS is different from the FAS).

If a patient is treated with a non-permitted treatment during the study period, then all efficacy variables measured after the intake of these not-allowed treatments will be censored for the efficacy analyses. Assessments of primary and secondary criteria after a forbidden treatment will be flagged in all listings.

The following treatments are not allowed during the study.

- Plasma exchange, blood products or derivatives other than the study drug.
- Immunomodulatory or immunosuppressant agents (e.g. including but not limited to cyclophosphamide, cyclosporine, interferon- $\alpha$ , interferon- $\beta$ 1a, anti-CD20, alemtuzumab, aziathioprine, etanercept, mycophenolate mofetil, methotrexate and haematopoietic stem cell transplantation).
- Oral or systemic corticosteroids if administered with an increasing dosage or introduced at a dose higher than 10 mg daily prednisolone or equivalent. Topical corticosteroids are permitted.
- Loop diuretics administered during the last 24 hours before an IVIg infusion.

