#### 4.6.1 Primary Efficacy Endpoint

The primary efficacy criterion is *response* of the patients at EOS visit. A patient is defined as having a *response* (or being a *responder*) both conditions below are fulfilled.

- The patient's adjusted INCAT disability score did not increase by more than 1 between baseline and EOS visit.
- The patient's CIDP treatment was not changed between baseline and EOS visit.

A change in CIDP treatment is defined by any of the following conditions:

- Increase/decrease of the dose (g/kg) of the study treatment by 5%
- Decrease of the time between courses
- Addition of corticosteroids (equivalent of more than 10 mg/day of prednisone for more than 10 days) or immunosuppressive drugs. As this condition is not possible to derive by programming, the study physician will review all treatments with corticosteroids and immunosuppressive drugs prior to database lock and flag those who fulfil the condition
- Premature discontinuation of study drug due to insufficient response to IMP and start of other CIDP treatments such as IVIg (other than study drug), corticosteroids, immunosuppressive drugs or plasma exchange

The primary analysis of the primary efficacy criterion will be done using the baseline and last available assessment of the adjusted INCAT disability score after the first study drug administration. That is, if the score at EOS visit is missing, then the Last Observation Carried Forward (LOCF) approach will be applied and the last available adjusted INCAT disability score will replace the missing value at EOS visit.

Similarly, if the assessment of the adjusted INCAT disability score is censored due to an intake of a forbidden treatment, the adjusted INCAT disability score from the last assessment before the intake of the forbidden treatment is used as replacement for the assessment of the EOS visit.

The number and percentage of Responders at EOS will be presented with descriptive statistics. The associated exact 95% Clopper-Pearson confidence interval (CI) will be calculated for the proportion of Responders.

The primary analysis will be performed using the FAS and a sensitivity analysis will be performed using the PPS.

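### SAP 4.6.1 counts plasma exchange or non-study immunoglobulin as a CIDP treatment change only after a stop for insufficient response, so some patients given either before the EOS assessment can be scored responders

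*SAP*

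**What the plan says.** Protocol 3.2.1, repeated in 12.9.1.1, has two responder branches. The first is "No change or decrease in the adjusted INCAT disability score and without any change in CIDP treatment between baseline and EOS visit". The second is "An increase by 1 point in the adjusted INCAT disability score without requirement of any change in CIDP treatment between baseline and EOS visit". Neither refers to why a patient stopped.

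SAP 2.5.1 and 4.6.1 restate this as two conditions that must both hold. The score condition is "The patient's adjusted INCAT disability score did not increase by more than 1 between baseline and EOS visit". The treatment condition is that CIDP treatment was not changed, and the SAP closes that term: "A change in CIDP treatment is defined by any of the following conditions". Four items follow:

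1. a 5% change in the per-kg dose of study drug;
2. a shorter time between courses;
3. added corticosteroids above a dose-and-duration threshold (over 10 mg/day prednisone equivalent for over 10 days), or immunosuppressive drugs;
4. "Premature discontinuation of study drug due to insufficient response to IMP and start of other CIDP treatments such as IVIg (other than study drug", with the list of treatments going on to corticosteroids, immunosuppressive drugs and plasma exchange.

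Three other rules matter. The SAP 4.6 list of forbidden treatments includes "Plasma exchange, blood products or derivatives other than the study drug". Efficacy values after such an intake are censored, and for the EOS value SAP 4.6.1 says that "the adjusted INCAT disability score from the last assessment before the intake of the forbidden treatment is used as replacement". SAP 3.2 also makes a patient withdrawn for lack of efficacy a non-responder. The stop reasons in SAP 4.1 are "AE, Protocol deviation, Withdrawal of consent, Lost to follow-up, Insufficient response to IMP, Other".

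**The concern.** Needing a different CIDP treatment is one of the ways in which a reduced maintenance dose fails. Under the SAP, receiving plasma exchange or another immunoglobulin counts as failure only if the stop also carries one particular disposition code. Otherwise the treatment leads to censoring, and the patient is judged on the last score before it was given. The primary responder rate would then depend partly on how a stop was coded, and the error runs only upward. The list is also uneven: a 5% dose change counts as a treatment change, while plasma exchange during study treatment does not.

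**Working it through.** The documents state no figure for this rule, so there is nothing to reproduce. The check has two parts.

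**Part 1: apply both rules to another CIDP treatment given before the EOS assessment.** The SAP rule is 4.6.1 plus 3.2; the protocol rule is 3.2.1. Score change means the last adjusted INCAT before intake minus baseline.

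| Stop reason | Treatment given before EOS | Score change | SAP | Protocol |
|---|---|---|---|---|
| Insufficient response | any | any | non-responder | non-responder |
| Other reason, or no stop | plasma exchange or non-study Ig | 0 or less, or +1 | **responder** | **non-responder** |
| Other reason, or no stop | plasma exchange or non-study Ig | +2 or more | non-responder | non-responder |
| Other reason, or no stop | immunosuppressant, or corticosteroid above the item 3 threshold | any | non-responder | non-responder |

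Only the second row differs. In that row:

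- Items 1 and 2 concern study drug only.
- Item 3 does not extend to immunoglobulin or plasma exchange. Item 4 names IVIg, immunosuppressive drugs and plasma exchange separately, and SAP 4.1 also lists IVIg apart from immunosuppressive agents.
- Item 4 needs a stop for insufficient response, and so does the rule in SAP 3.2.
- The study physician's review before database lock (item 3) covers corticosteroids and immunosuppressive drugs only.

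The SAP can also disagree with itself. In SAP 4.6.2, a 1-point increase plus an investigator's judgement that treatment must change is a relapse. If that patient's stop is not coded as insufficient response and none of the four items applies, the same patient is a relapse in the Kaplan-Meier analysis and a responder in the primary analysis.

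**Part 2: size.** Protocol 12.3 expects 15 to 30 patients. Moving one patient changes the rate by 1/n: 1/30 = 3.3 percentage points and 1/15 = 6.7 points.

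To show the effect on the planned Clopper-Pearson interval, starting rates have to be assumed. I took 1 minus the relapse rates that Protocol 1.1.2 cites from the 24-week extension of a placebo-controlled IVIg trial (13% on IVIg, 45% on placebo), giving 87% and 55%. These mark a range and are not predictions for this study. Counts: 0.87 × 15 = 13.05, taken as 13; 0.87 × 30 = 26.1, taken as 26; 0.55 × 15 = 8.25, taken as 8; 0.55 × 30 = 16.5, taken as 16. The number of affected patients (0, 1 or 2) is also assumed.

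| Assumed start, as the SAP scores it | One patient moved | Two patients moved |
|---|---|---|
| 13/15 = 86.7% (59.5–98.3) | 12/15 = 80.0% (51.9–95.7) | 11/15 = 73.3% (44.9–92.2) |
| 26/30 = 86.7% (69.3–96.2) | 25/30 = 83.3% (65.3–94.4) | 24/30 = 80.0% (61.4–92.3) |
| 8/15 = 53.3% (26.6–78.7) | 7/15 = 46.7% (21.3–73.4) | 6/15 = 40.0% (16.3–67.7) |
| 16/30 = 53.3% (34.3–71.7) | 15/30 = 50.0% (31.3–68.7) | 14/30 = 46.7% (28.3–65.7) |

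**The case against.** A reader might infer that every patient treated outside a stop for insufficient response becomes a responder, or that everyone who leaves early and returns to immunoglobulin is misclassified. The documents support neither.

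- Item 3 catches immunosuppressants and above-threshold corticosteroids whatever the stop reason, a carried score of +2 or more fails anyway, and SAP 3.2 fails any withdrawal for lack of efficacy.
- Protocol 3.1.5, 3.1.6 and 8.2.5 place the EOS assessment before any other CIDP treatment. Immunoglobulin started after that visit lies outside the baseline-to-EOS window in the protocol too. A patient who stops for an adverse event with an unchanged score and then goes back to another product is a responder under the first protocol branch as well.
- Censoring and carry-forward are not SAP inventions; they come from Protocol 12.9.1.1 and 12.9.1.3.
- What remains is largely protocol deviations. They are reviewed at the data review meeting (SAP 3.5.2) and flagged in listings (SAP 4.6).
- The analysis is descriptive, and SAP 4.10 already reports early termination because of relapses, so a few reclassified patients are unlikely to reverse that message.

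All of this stands and limits the reach. It does not close the gap. Flagging does not change how a patient is scored in the FAS, and the PPS at most drops such a patient, if the deviation is classed as major; it does not score a failure. Inheriting carry-forward from the protocol explains which score is used, but it does not explain why the treatment itself is not counted as a change.

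**Conclusion.** The point holds in a narrow form. It concerns patients given plasma exchange or non-study immunoglobulin before the EOS assessment, not coded as stopped for insufficient response, whose last score before intake is no more than 1 point above baseline. For them the SAP reverses the protocol's classification on the primary endpoint, and SAP 4.10 does not list this among the changes to planned analyses.

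The bias can only raise the responder rate, by 3.3 to 6.7 points per patient at n=30 to n=15. The number of such patients is not in the documents and may be zero, so the total effect is unknown.

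Two assumptions apply. The patient needs an INCAT assessment after first dose and before intake; without one, the patient may fall out of the FAS instead. And SAP 4.6.1 is taken to govern which score is used. SAP 3.5.1 limits censoring to a half-life-based window still to be adjudicated, so a later score might count again. Even then none of the four conditions would be triggered.

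**What to change.** Before database lock, in SAP 2.5.1 and 4.6.1:

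- Add a stand-alone condition: any plasma exchange or non-study immunoglobulin given for CIDP between first dose and the EOS assessment is a change in CIDP treatment, whatever the discontinuation reason.
- State that this takes precedence over LOCF and over replacement of a censored score.
- Do not count treatment that is merely planned at EOS. That would turn stable patients who stop for an adverse event, or because the sponsor ended the study, into non-responders, which the first branch of Protocol 3.2.1 does not require. The one exception is a patient at +1 for whom the investigator judged a CIDP treatment change to be required; the second branch already makes that patient a non-responder.
- Reconcile the censoring window in SAP 3.5.1 with SAP 4.6 and 4.6.1, which mention none.
- Record the clarification in SAP 4.10.

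The cost is SAP wording and a slightly wider pre-lock medication review. Concomitant medication (Protocol 7.2) and CIDP treatment changes at discontinuation (Protocol 5.4) are already collected. The responder rate may come out slightly lower.

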#### **3.1.5. Follow-up and End of Study**

Three weeks after visit V16, patients will undergo an EOS visit. This visit corresponds to visit V17 (Week 48).

In the event of premature discontinuation of the study drug or patient withdrawal from the study, an EOS visit will be performed within 7 days and prior to administration of any other treatment for CIDP (see Section [8.2.5](#)). The reason for premature study drug discontinuation / study withdrawal should be accurately documented, as well as the planned new treatment to be administered if any.

The total duration of the study for a patient is approximately 48 weeks.

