### **3.1.6. Relapsing Patients**

A relapse is defined as one of the following conditions:

- Adjusted INCAT disability score increase by 1 point compared to baseline,  
AND  
Judging on the clinical examination and/or the neurological scales assessments, the Investigator considers change in patient's treatment is mandatory: increase in IVIg dosage, increase or initiation of a corticotherapy, immunosuppressive therapy, plasma exchange.
- Adjusted INCAT disability score increase by at least 2 points compared to baseline.

Relapsing patients will undergo the study assessments scheduled at the EOS visit within 7 days and prior to the administration of any other CIDP treatment. The patient will be then withdrawn from the study and treated at the discretion of his/her physician.

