#### ***12.9.1. 3. Handling of Missing Data***

The primary analysis of the primary variable will be done using the baseline and last available assessment of the adjusted INCAT disability score. If the score at EOS visit is missing, then the Last Observation Carried Forward (LOCF) approach will be applied and the last available adjusted INCAT disability score will replace the missing value at EOS visit.

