#### 3.2 HANDLING OF MISSING DATA AND OUTLIERS

Regarding the primary criterion, a patient will be also considered as a non-responder if the patient is withdrawn due to lack of efficacy of the treatment (insufficient response to the investigational medicinal product [IMP]). If the INCAT score at EOS visit is missing, then the Last Observation Carried Forward (LOCF) approach will be applied and the last available adjusted INCAT disability score will replace the missing value at EOS visit.

The LOCF approach will also be used to handle the missing data of secondary endpoints.

When AEs are documented in the diary, date-time of AE onset may be missing or incomplete. As a result, it might not be possible to determine if the AE started between the start of an infusion until 72 hours after the end of the infusion (Temporally Associated AE [TAAE]). In such cases, the response to the question "Did the

AE start within 72 hours of an infusion” will be used for determining if the AE is temporally associated to an infusion or not.

Partial dates of first symptoms and partial dates of diagnosis (collected in the I10E-1302 study) will be imputed by 15 if only the day is unknown and by 1st July if day and month are unknown. No imputation will be done if the year is unknown.

For the calculation of duration of AEs, partial start and end dates will be imputed with the first and last possible date within the period defined by the partial date, respectively. In general, no calculation of duration will be made if either the start date or stop date is missing, i.e., can't be imputed using pre-determined rules.

No other general rules for the replacement of missing data are planned.

Data listings will always show the original CRF reported values and not the imputed values.

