##### 2) Time to relapse

Relapse is defined as as one of the following conditions:

- Adjusted INCAT disability score increase by 1 point compared to baseline

AND

Judging on the clinical examination and/or the neurological scales assessments, the Investigator considers change in patient's treatment is mandatory: increase in IVIg dosage, increase or initiation of a corticotherapy, immunosuppressive therapy, plasma exchange.

- Adjusted INCAT disability score increase by at least 2 points compared to baseline.

Time to relapse (measured from the first IMP infusion in I10E-1306) will be analysed using a Kaplan-Meier (KM) method. Patients without relapse will be considered censored at their last assessment of the INCAT disability score. Patients with a forbidden treatment intake before a relapse will be considered censored at the date of the first intake of a forbidden treatment.

KM estimates of the mean, the median as well as for the first and third quartile will be provided together with their associated 95% confidence interval. A KM-plot will be provided showing the incidence of relapse over time. Time of censoring will be displayed in the graph. A table will be included below the graph showing the number of patients "at risk" (i.e. without relapse), the number of patients with a relapse and the number of censored patients at the time points 0, 12, 24, 36 and 48 weeks.

Descriptive statistics will be provided for the time to relapse on the subset of patients with relapse until EOS.

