#### 4.10 CHANGES IN THE CONDUCT OF THE STUDY OR PLANNED ANALYSIS

Early assessment of study results showed a remarkable percentage of patients who demonstrate CIDP relapse at the tested lower dose. It was decided then to early terminate the study in the interest of the patients and according to good clinical practices. This rationalized the presentation of the efficacy results to focus on key efficacy endpoints.

Results for response rate at 24 weeks, MRC 12 muscles sum score, Rasch-modified MRC sum score, Percentage of patients without change in CIDP treatment from baseline to 24 weeks and EOS visit, and patient and investigator CGI will be presented in listings.

Patient level and course/infusion level information will be provided for exposure, laboratory, and vital signs parameters.

Analysis of laboratory data may involve standardization procedure contingent on the evaluation of the sparseness of laboratory data, the completeness of the local laboratories' normal ranges, and the choice of the standard normal ranges prior to database lock. Liver function test results will be examined to identify Hy's Law, Temple's Corollary, and elevated test result cases.

Analysis of biomarker data will not be performed. Instead the data will be listed using FAS.

Planned analysis associated with the ultrasonography ancillary study will not be performed due to non-collection of required data.

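### The Week 48 responder rate is scored from the last available INCAT score with no minimum follow-up, so relapse-free patients cut off by the early termination count as responders, and no planned analysis corrects for this

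*SAP*

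**What the plan says.** Protocol 3.1.5 places the EOS visit at V17, Week 48, three weeks after the last of 16 courses. Protocol 3.2.1 makes the responder rate at that visit the primary endpoint.

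SAP 4.6.1 defines a responder as a patient whose adjusted INCAT score rose by no more than 1 point from baseline and whose CIDP treatment did not change. On which score to use, it says: "The primary analysis of the primary efficacy criterion will be done using the baseline and last available assessment of the adjusted INCAT disability score", meaning any assessment after the first dose. The rule comes from Protocol 12.9.1.3: "If the score at EOS visit is missing, then the Last Observation Carried Forward (LOCF) approach will be applied".

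A patient who stops early need not have a missing EOS score at all. Protocol 3.1.5 says: "In the event of premature discontinuation of the study drug or patient withdrawal from the study, an EOS visit will be performed within 7 days". (Protocol 8.2.5 gives 72 hours for the same visit; the two must be reconciled.)

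Only one kind of early exit is set to failure. SAP 3.2 says "a patient will be also considered as a non-responder if the patient is withdrawn due to lack of efficacy of the treatment", and the treatment-change list in SAP 4.6.1 counts a premature stop only when it is for insufficient response and another CIDP treatment is started. On relapse, Protocol 3.1.6 says: "The patient will be then withdrawn from the study and treated at the discretion of his/her physician".

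SAP 4.10 then reports a notable share of relapses at the reduced dose and adds: "It was decided then to early terminate the study in the interest of the patients". It cuts back several efficacy outputs, including the 24-week responder rate, which is now only listed. It does not touch the primary scoring rule.

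**The concern.** The EOS label covers two different things: a patient observed to Week 48, and a patient whose observation ended when the sponsor stopped the study, possibly after a few weeks. Both count as responders if the last score is acceptable and CIDP treatment was unchanged. The same holds for patients who leave early because of an adverse event, withdrawal of consent or loss to follow-up.

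The direction follows from the design. Relapse ends participation, and treatment changes accumulate from baseline onwards, so a patient can only move from response to failure as follow-up lengthens. Cutting follow-up short removes the opportunity to fail. This matters in a study stopped because patients were relapsing: its headline figure would credit the reduced dose with the relapses that were not observed.

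**Working it through.** The plan states no target rate, power or expected responder rate, so there is no figure of its own to reproduce. The check has three parts.

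**1. Does any planned output show the effect?**

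- The only sensitivity analysis of the primary endpoint repeats it on the PPS, and SAP 4.6 runs it only if the PPS differs from the FAS. The scoring rule is the same.
- The Kaplan-Meier analysis of time to relapse (SAP 4.6.2) does censor these patients. Its specified estimates are: "KM estimates of the mean, the median as well as for the first and third quartile will be provided", with 95% confidence intervals. There is also a plot, and "A table will be included below the graph showing the number of patients" at risk, relapsed and censored at 0, 12, 24, 36 and 48 weeks. No relapse-free proportion with a confidence interval is specified at a fixed week.
- The Kaplan-Meier event is also not the complement of response. SAP 4.1 allows withdrawal for insufficient response on the basis of grip strength, R-ODS, MRC or CGI. Such a patient without an INCAT relapse is a non-responder in the primary analysis but is censored in the Kaplan-Meier analysis.

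**2. Expected size under stated assumptions**

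Inputs:

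- 24-week relapse r of 13% and 45%. Protocol 1.1.2 gives these for the IVIg (1 g/kg) and placebo arms of one cited trial. They are used only to span a range.
- Assumed: constant hazard; non-response is the same as relapse; a fraction f of patients has possible follow-up ending uniformly over 0 to 48 weeks.

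True Week 48 relapse-free rate: S = (1 − r)².

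Probability that a patient with limited follow-up is scored a responder: E = (1 − S)/(−ln S).

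Expected rate under the SAP rule: (1 − f)·S + f·E.

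- r = 0.13: S = 0.87² = 0.757; E = 0.243/0.2785 = 0.873.
- r = 0.45: S = 0.55² = 0.3025; E = 0.6975/1.1957 = 0.583.

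| r | S (true) | f | SAP rule | Excess (points) |
|---|---|---|---|---|
| 0.13 | 75.7% | 0.2 | 78.0% | 2.3 |
| 0.13 | 75.7% | 0.5 | 81.5% | 5.8 |
| 0.45 | 30.3% | 0.2 | 35.9% | 5.6 |
| 0.45 | 30.3% | 0.5 | 44.3% | 14.0 |

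Here f is the share whose possible follow-up is short, not the share actually cut off relapse-free. The latter is f·E: 17% and 44% at r = 0.13, and 12% and 29% at r = 0.45.

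A simulation with 20 patients, visits every three weeks and f of 0.2 and 0.4 agrees. The SAP rule gave 0.780 and 0.808 (true 0.757), and 0.365 and 0.424 (true 0.303). The Kaplan-Meier estimate at Week 48 stayed on target, at 0.755 and 0.758, and at 0.305 and 0.302.

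For a single non-efficacy dropout at Week 24 who is relapse-free, the chance of failing by Week 48 is r. The expected addition to the rate is r/n: 0.13/30 to 0.45/30, or 0.4 to 1.5 points, with 30 patients; 0.9 to 3.0 points with 15.

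**3. A counted example (assumed numbers)**

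Take 20 patients, of whom 8 relapse.

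- With 4 cut off relapse-free and 8 completing, the SAP rule gives 12/20 = 60.0% (95% CI 36.1 to 80.9).
- With 8 cut off and 4 completing, it gives the same 60.0%.
- Dropping the cut-off patients gives 8/16 = 50.0% in the first case and 4/12 = 33.3% in the second. Counting them as failures gives 8/20 = 40.0% and 4/20 = 20.0%.

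The reported figure cannot distinguish the two situations. Neither alternative is a good replacement: counting the cut-off patients as failures is a lower bound, and dropping them keeps every relapser while removing patients who were still relapse-free.

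**The case against.** The last-available rule was in the protocol before the termination. The study is descriptive, with no hypothesis or decision threshold, and the SAP discloses why it stopped. The number cut off is not given, and the 14-point upper figure needs a placebo relapse rate together with half the patients having short follow-up. With 15 to 30 patients expected, the Kaplan-Meier counts, exposure summaries and discontinuation listings would let a careful reader see truncation patient by patient. The PPS might exclude truncated patients, because the deviation specification is a separate document. A Kaplan-Meier proportion would not isolate truncation either, since the primary endpoint also fails patients for a 5% dose change, a shorter interval between courses or added corticosteroids or immunosuppressants.

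Much of this stands as a limit on size. The magnitude is illustrative, and the net error of the reported rate is unknown because those other responder rules can push it down. The point about event definitions is also right, which is why a restricted responder rate using the primary definition is needed alongside the Kaplan-Meier figure. It does not remove the gap. The SAP was written with the termination known and left the rule as it was. Counts and listings are not a fixed-week estimate with an interval, and nothing in the documents says the PPS removes these patients. Descriptive status does not excuse a Week 48 label on a result with mixed follow-up.

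**Conclusion.** The concern holds and should be fixed. Patients who are relapse-free when stopped early are scored as EOS responders whatever their follow-up, provided CIDP treatment was unchanged. Relative to Week 48, truncation can only leave the rate unchanged or raise it. That direction rests on the documents alone. The size, about 2 to 14 points, rests on the assumed relapse range, constant hazard, uniform cut-off and 20% to 50% of patients with limited follow-up; it is not an estimate for this trial. No planned analysis gives a fixed-week proportion, with a confidence interval, that allows for the truncation.

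**What to change.** Keep the pre-specified crude rate with its Clopper-Pearson interval as the primary result. Add to SAP 4.6.1 and 4.6.2, as supplementary:

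- **Kaplan-Meier event-free proportions at Weeks 24 and 48 with 95% CI.** The event is relapse as defined in SAP 4.6.2 or withdrawal for insufficient response; sponsor termination is administrative censoring.
- **The responder rate, with the primary definition, restricted to patients first dosed at least 48 weeks before the termination date.** Show non-efficacy dropouts both as observed and as non-responders. Selection is by entry date, not outcome, so comparison with the crude rate shows the effect of truncation. State whether the 7-day visit window is added to the cut-off.
- **The V9 (Week 24) responder rate, tabulated with its Clopper-Pearson interval** for patients first dosed at least 24 weeks before termination, instead of only listed.

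In SAP 4.1, show sponsor termination as its own discontinuation reason; this is presentational but gives the count directly. State in SAP 4.10 that these analyses were added after the early results were seen.

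The cost is SAP wording and a few output rows from data already collected. The added figures may be less favourable and will be imprecise: at a 40% rate the Clopper-Pearson interval is 23% to 59% with 30 patients (12/30) and 16% to 68% with 15 (6/15), and wider if fewer patients qualify.
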